TITLE: KRONOS Versus Breg T-Scope Post-operative Knee Braces Following Anterior Cruciate Ligament (ACL) Reconstruction
NCT07090616
DATE: 29 April 2025

PROTOCOL TITLE: A Randomized Controlled Trial of the KRONOS Versus Breg T-Scope Post-operative Knee Braces Following Anterior Cruciate Ligament (ACL) Reconstruction

PRINCIPAL INVESTIGATOR:

Name: [name], PhD. [name]

[contact]

Email Address: [contact]

VERSION DATE: 04/25/2025

STUDY SUMMARY:

Investigational Agent-s	None
-Drugs or Devices	
IND / IDE / HDE #	N/A
	Children
	Children who are wards of the state
	Adults Unable to Consent
Indicate	Cognitively Impaired Adults
Special Population-s	☐ Neonates of Uncertain Viability
	Pregnant Women
	Prisoners -or other detained/paroled individuals
	☐ Students/Employees
Sample Size	40
Funding Source	Department of Orthopedic Surgery
	Written Main and Assent Form
Indicate the type of consent	Verbal/Waiver of Documentation of Informed Consent
to be obtained	Waiver of HIPAA Authorization
	Waiver/Alteration of Consent Process
Site	Single Site Research Study
Site	Data Coordinating Center -DCC
Research Related Radiation	Yes
Exposure	∑ No
DSMB / DMC / IDMC	Yes
DOME / DIVIC / IDIVIC	⊠No

Version 2.0: 4/25/2025 Page 1 of 11

ACRONYMS & ABBREVIATIONS:

ACL- Anterior Cruciate Ligament

BMI- Body Mass index

IKDC- International Knee Documentation Committee

KOOS-Knee Injury and Osteoarthritis Outcome Score

MOR – Midwest Orthopedics at Rush

MRI – Magnetic Resonance Imaging

PRO – patient reported outcome

PROMIS-Patient-Reported Outcomes Measurement Information System

ROM – Range of Motion

RTS- Return to Sport

RTW-Return to Work

RUMC – Rush University Medical Center VAS pain- Visual Analog Pain Scale VR/SF 12-Veteran RAND 12-Item Health Survey

Purpose of the study -

The purpose of this study is to evaluate the clinical efficacy of the KRONOS postoperative knee brace compared with the standard Breg T-scope hinged brace following anterior cruciate ligament (ACL) reconstruction surgery.

Background & significance –

Anterior cruciate ligament (ACL) injuries of the knee are prevalent and frequently treated with surgical reconstruction of the ligament using a graft to restore knee function and stability. Postoperatively, early rehabilitation is critical to successful surgical outcomes, preventing postoperative complications, and returning to an active lifestyle. However, care must also be taken to protect the implanted graft against strain that may disrupt tendon-to-bone healing, and ultimately cause premature failure of the graft. Consequently, over 60% of surgeons who perform ACL reconstruction recommend and prescribe rehabilitative postoperative knee braces locked in extension to limit extension/flexion motion, varus and valgus (inward and outward) movements at the knee, and help patients regain extension range of motion (ROM.²

Despite widespread clinical use, evidence on the efficacy of current bracing technologies remains controversial and inconclusive. Some randomized controlled trials and systematic reviews have concluded that rehabilitative bracing provided no clinical benefit with respect to knee ROM, knee laxity, pain, or quadriceps (large thigh muscle group) strength in the early postoperative period or at mid-term follow-up.^{2–4} In contrast, Melegati et al⁵ demonstrated improved extension after one week postoperatively among a group that used a rehabilitative brace locked in full extension, compared to a group that

Version 2.0: 4/25/2025 Page 2 of 11

used the same brace locked from 0-90°. This variability may be in part due to significant limitations present across several of the previous studies, including lack of compliance data and power calculation to determine necessary sample sizes.² ⁶

The KRONOS postoperative unloader brace features a new bracing technology that combines the capability of hyperextension immobilization with additional benefits of offloading up to 60 lbs off the knee joint. The adjustable tensioning system in the KORNOS brace offers promising potential to significantly alleviate patient discomfort and pain, facilitate quicker return to a higher level of activity, and ultimately contribute to improved surgical outcomes. The primary purpose of this study is to evaluate the clinical efficacy of the KRONOS postoperative unloader knee brace compared with standard Breg T-scope hinged brace in improving range of motion and other complications following anterior cruciate ligament (ACL) reconstruction surgery.

Hypothesis

We hypothesize that subjects randomized to receive the KRONOS postoperative unloader knee brace will reach full extension sooner and have reduce extension deficits compared to subjects randomized to receive the standard Breg T-scope hinged brace. In addition, it is hypothesized that the KRONOS subjects will require fewer additional treatments for extensions deficits including, but not limited to, additional therapy, intra-articular injections, oral corticosteroids, manipulation under anesthesia, or arthroscopic revision surgery.

Selection of Subjects –

Patients scheduled to undergo primary ACL reconstruction as indicated via CPT 29888 from the Athena electronic medical record (EMR) will be identified and eligible for enrollment in this study. Following the informed consent process outlined below, we will prospectively enroll and randomize 20 participants to one of the two study arms (KRONOS versus Breg T-scope post-operative knee brace), totaling 40 participants in each group.

Inclusion Criteria:

- Subjects > 18 years of age
- English-speaking
- Scheduled to undergo primary anterior cruciate ligament reconstruction surgery
- No history of prior knee surgery on the operative knee
- No concomitant ligamentous repair or reconstruction procedures (i.e. ligamentous pathology aside from anterior cruciate ligament).
- Subjects undergoing concurrent partial meniscectomy or meniscus repair that would not alter postoperative weight-bearing status or rehabilitation protocol would be eligible for inclusion.

Version 2.0: 4/25/2025 Page 3 of 11

• Clinical and radiographic examination (MRI) consistent with an acute full thickness ACL tear

Exclusion Criteria:

- Age < 18 years of age
- Non-English speaking
- Revision ACL reconstruction
- Multi-ligamentous injury, including concomitant posterior cruciate ligament, medial collateral ligament and fibular collateral ligament injuries
- Concomitant meniscal or cartilage injury that would alter postoperative weight bearing status or rehabilitation protocol
- Inability to comply with the proposed follow-up clinic visits
- Subjects lacking decisional capacity
- Worker's compensation subjects
- Requiring a custom-sized brace

Consent process -

Potential participants are identified using medical chart and case review. The study eligibility requirements will be reviewed by the PI and study staff. The potential participant is pre-selected as tentatively meeting the eligibility requirements for the study. Research study staff will reach out to eligible patients through a phone call explaining the study. Randomization to the treatment (KRONOS postoperative brace) or control group (Hinged knee brace) will occur at the time of informed consent

Informed Consent Discussion

Investigator and/or PI and research study staff will contact the patient in clinic or via telephone to discuss the research study with them. Ideally, the informed consent discussion should be conducted when the study staff and potential participant has time to ask and answer questions. Information provided to the patient includes the rationale for the study procedure or treatment, the number of study visits and the study activities they will need to complete, risks involved, expected benefits, and alternatives to treatment.

The process may occur over a period of several discussions, culminating in the signing of a consent form in the office (Ipad or paper) or sent to their verified email address. The informed consent discussion will be documented in the patient profile or chart.

If the patient agrees to participate, their email addressed will be verified. The consent will be obtained electronically sent through the secured platform called Patient IQ to their email. The potential subject will then be prompted to reply with the appropriate passcode in order to access the consent form, and then provide the passcode again with their

Version 2.0: 4/25/2025 Page 4 of 11

signature (secured). No research activities will be performed prior to execution of the consent. A copy of the time stamped document will be sent to the study team through the electronic platform and a copy will be sent to the participant.

Study Design & Procedures-

This is a randomized controlled trial.

We estimate 40 participants (20 Kronos: 20 T-Scope) will be enrolled in the study.

Primary outcome variable

• Rates of extension deficit (as measured by the fraction of patients with reduced extension compared to the contralateral knee, determined by heel height and goniometric measurements of knee extension)

Bracing Protocol

Both treatment groups will progress according to a standard of care postoperative rehabilitation program regardless of the group to which the patient is randomized.

KRONOS Bracing Group

Subjects randomized to the treatment group will be measured and fitted with the KRONOS knee brace at their initial clinic visit after study enrollment. The patient will be instructed to use the brace preoperatively and bring it to their surgery, after which the brace will be placed again on the patient postoperatively at the conclusion of their procedure. Subjects will be instructed to wear the brace until symmetric terminal extension is achieved as indicated by side-to-side comparison with the non-surgical limb. This will be under the supervision and approval of the providing physician. Subjects will be instructed to use the brace (locked in extension and under high tension) at night during sleep and ambulation, though removal for therapy and rehabilitation exercises will be permitted.

Control Group – Standard Breg T-Scope Postoperative Bracing

Subjects will be placed in a standard postoperative hinged knee brace in the operating room that will be locked in full extension. Subjects will be instructed to use the brace locked in extension while sleeping for 6 weeks and when ambulating until the patient is able to perform a straight leg raise with no extension lag outside of the brace, at which point the brace may be worn unlocked during ambulation.

Table 1. Study timeline.

Preop Surgery 2 6 weeks 12 6 months 12

Version 2.0: 4/25/2025 Page 5 of 11

			weeks		weeks		months
Patient Recruitment	•						
Informed Consent and Randomization Physical Exam (i.e. Heel height and	•						
goniometer measurement of active	•	•*	•	•	•	•	
extension, passive flexion, passive extension)							
Circumferential thigh							
measurement (including healthy	•		•	•	•	•	
knee at pre-op)							
Brace Placement	•**	•					
PROMs	•				•	•	•
Brace compliance survey	1 .	•**	•	•	.1	. 1	

^{*}Passive flexion and extension ROM only under anesthesia prior to beginning surgery

PROMs will include: IKDC, KOOS, VR-12, PROMIS Depression, PROMIS Physical Function, PROMIS Pain Interference, Return to Sport (RTS) and Return to Work (RTW), Resilience scale and brace compliance survey.

Study Interventions –

Prospective Data Collection

Timeline of Events

- 1. Once subjects are indicated for ACL surgery, a review of inclusion criteria will be undertaken, and subjects will be offered the opportunity to participate in the study.
- 2. Pre-operative physical exam findings including Pivot-shift, Lachman, and range of motion data will be recorded.
- 3. Range of motion measurements (ROM), including heel height^{7,8} and goniometric measurements of 3 types of ROM (active extension, passive flexion, and passive extension) will be done at the initial visit, preoperatively on the day of surgery, *intraoperatively under anesthesia before the initiation of the surgery* (passive flexion and passive extension only), and at the designated postoperative timepoints indicated in Table 1 (1 week, 2 week, 6 week, 12 weeks, 6 months, and 12 months).
- 4. Thigh circumference will also be measured with tape measure at the mid-thigh and

Version 2.0: 4/25/2025 Page 6 of 11

^{**} Only for patients randomized to the KRONOS brace treatment group

suprapatellar levels on the operative knee as a surrogate for quadriceps atrophy, as previously done^{10–12}, pre-operatively and at the designated postoperative visits in Table 1 (1 week, 2 week, 6 week, 12 weeks, 6 months, and 12 months). Thigh circumference of the nonoperative healthy knee will also be measured pre-operatively for baseline comparison

- 5. Informed consent will be obtained. Prior to surgery (preoperative) subjects will be asked to complete standard of care patient reported outcomes questionnaires including IKDC, KOOS, PROMIS (Depression, Pain Interference, Physical function), VAS pain, VR/SF 12, RTS, RTW and brief resilience scale.
- 6. Brace compliance survey A survey assessing patient compliance with bracing instructions will be administered at the designated postoperative timepoints indicated in Table 1.
- 7. Subjects will proceed with operative management of their ACL tear, including appropriate treatment and documentation of concomitant injuries.
- 8. Subjects will be appropriately fitted for the brace corresponding to randomization on the day of surgery. All braces will be placed on the subject in the operating room at the conclusion of the procedure. All subjects will begin a standard of care physical therapy protocol on postoperative day 1-14.
- 9. Subjects will undergo standard of care follow up at 1-week, 2-week, 6-weeks, 12-weeks, 6-months, and 12 months. At these standard of care visits, range of motion, including goniometric angle and heel-height measurements, will be made at all postoperative time points.

 Time-to-achievement of full symmetric extension relative to the non-surgical knee will be monitor and recorded. Additional physical exam of the knee will be performed at all follow-up time points.
- 10. At 12 weeks, 6 months, and 12 months, subjects will also be asked to complete standard of care patient reported outcomes questionnaires including IKDC, KOOS, PROMIS, VAS pain, VR/SF 12, and brief resilience scale. Subjects will also be asked to answer standard of care questions regarding return to work and return to sport throughout the 1-year postoperative period.

Retrospective Data Collection

The following data will be abstracted from secured electronic medical record databases (Epic, Athena, Opal, Patient IQ) and electronically recorded on coded data collection tool for this study:

- Demographic information (age, sex, body mass indes (BMI), laterality)
- Chief Complaint
- History of present illness

Version 2.0: 4/25/2025 Page 7 of 11

Physical Exam

Opal and Joints will be used to capture the following:

Surgical approach

Arthroscopic diagnoses

Techniques used

Fixation device / technique

Preoperative imaging including but not limited to MRI

The following outcome variables will be taken from Athena and Patient IQ:

- Postoperative complications
- Failure of primary reconstruction
- Need for a revision or subsequent procedure
- Preoperative / postoperative patient reported outcomes (PRO) including:

IKDC, KOOS, VR-12, PROMIS Depression, PROMIS Physical Function, PROMIS

Pain Interference, Return to Sport (RTS) and Return to Work (RTW), Resilience scale

Other outcomes variables of interest:

- Time-to-achievement of full extension
- Degree of extension loss
- Time to walking without a limp
- Quad circumference difference
- Frequency of brace use
- Number of postoperative physical therapy visits up to one year post-op
- Standard of care Breg T-scope group: time to unlocking the brace
- Kronos group: time to no quad assist (no dial engaged)

Rehabilitation Protocol

The rehabilitation program will be started on the day after surgery according to the providing physician's standard protocol.

Risk/benefit assessment –

There is no direct benefit to the patient for his/her participation in this study.

The results will contribute to the optimization postoperative bracing and rehabilitation protocols following ACL surgery. This study will help determine if the KRONOS postoperative knee brace is an efficacious and safe methodology to improve range of motion and reduce extension deficits following ACL reconstruction.

Version 2.0: 4/25/2025 Page 8 of 11

Potential risk may include having the participant's privacy or confidentiality compromised. The participant's identities will not be identifiable in publications resulting from this investigation. Every reasonable effort will be made to protect the participant's information while their data is used as part of this study.

The alternative to participation in this study is not to participate.

Costs to the subject—

A brace will be provided to each study participant free of cost regardless of what group they are in—a standard of care Breg T-Scope brace or a Kronos brace.

No insurance coverage will be offered for regularly scheduled standard of care postoperative visits. However, any additional visits scheduled solely for the purpose of this study will be covered at no cost to the patient.

Compensation of subjects-

No compensation will be offered to study participants.

Data Analysis and Statistical Considerations -

Power analysis was based on data published by Mikkelsen et al.⁶ as part of an ACLR randomized controlled trial of a hyperextension brace. A priori power analysis was conducted to determine the sample size required to detect a significant difference in the proportion of patients experiencing a loss of full knee extension of $\geq 2^{\circ}$ between the straight brace and hyperextension brace groups. Using the observed proportions from the study (p1=0.545 for the extension group and p2=0.091 for the hyperextension group), the following parameters were used in G*Power for the calculation: **Statistical test**: Fisher's exact test (two independent groups); **Effect size**: w=0.57; **Significance level** (α): 0.05; **Power** ($1-\beta$): 0.8. The analysis indicated that a total sample size of 32 **participants** (16 per group) would be required to achieve 80% power to detect a statistically significant difference in the proportions of patients experiencing knee extension loss at $\alpha=0.05$. To account for potential loss of subjects to follow-up, a total of 40 subjects will be eligible to be enrolled.

The statistical software *R* will be used for analyses and calculation of relevant p-values, standard deviation, correlation coefficients, and confidence intervals. Categorical variables will be analyzed via Chi-squared test, while quantitative variables will be analyzed via students' t-test for parametric data and Wilcoxon Mann-Whitney test for nonparametric data.

Data & Safety monitoring

Version 2.0: 4/25/2025

There is minimal risk to the subjects except the potential for loss of privacy and confidentiality, but every reasonable effort will be made to protect the patient's information while their data is used as part of this study.

Data storage & confidentiality –

Participant information will be collected and maintained in a excel data sheet housed on the Midwest Orthopedics at Rush (MOR) server, which is dual-factor authentication protected and accessible only to research staff. Subjects identity will be coded via the use of a separate document key (electronic excel spreadsheet) correlating subjects' Rush medical record numbers with a study ID assigned for the sole purpose of this study. This key electronic document will be maintained as a separate electronic file (excel spreadsheet) from data collection tool and will be housed in the Midwest Orthopaedics at Rush server, which is dual-factor authentication protected and accessible only to research staff.

Files will not be shared with non-study personnel.

According to (Rush policy OP-0432 and CC-G04) and study data must be maintained for 10 years in accordance with Illinois State Law. After this time the data will be destroyed by permanently and securely deleting electronic files on the Master key document (PHI) and the coded data collection tool.

References:

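### Allocation is drawn at consent and the order of the preoperative measures is not fixed, so questionnaires may follow knowledge of the arm and some extension readings may follow brace use in one arm only

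*Protocol*

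**What the plan says.** All references are to the protocol.

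- **Consent process.** "Randomization to the treatment (KRONOS postoperative brace) or control group (Hinged knee brace) will occur at the time of informed consent". Consent may be signed in the office or through an emailed link, so allocation can happen remotely. The same section adds: "No research activities will be performed prior to execution of the consent".
- **Bracing Protocol, KRONOS group.** "Subjects randomized to the treatment group will be measured and fitted with the KRONOS knee brace at their initial clinic visit after study enrollment". Then: "The patient will be instructed to use the brace preoperatively and bring it to their surgery".
- **Bracing Protocol, control group.** "Subjects will be placed in a standard postoperative hinged knee brace in the operating room that will be locked in full extension".
- **Table 1.** Consent with randomisation, the physical exam, thigh circumference, brace placement (marked as KRONOS only) and the questionnaires share one Preop column, with no order among them.
- **Timeline of Events, item 3.** Goniometer and heel-height readings "will be done at the initial visit, preoperatively on the day of surgery", and again under anaesthesia.
- **Timeline of Events, item 5.** "Informed consent will be obtained. Prior to surgery (preoperative) subjects will be asked to complete standard of care patient reported outcomes questionnaires".
- **Timeline of Events, item 8.** "Subjects will be appropriately fitted for the brace corresponding to randomization on the day of surgery".

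The primary outcome is the fraction of patients whose extension is reduced relative to the other knee. The protocol describes no blinding and does not say which preoperative reading is the baseline for extension or for the questionnaires.

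**The concern.** A baseline is useful because neither the treatment nor knowledge of the treatment can have touched it. Here allocation is tied to consent, and the questionnaires are listed after consent. In a trial without described blinding, knowing the arm can shift self-reported pain and function before surgery. Extension measured on the day of surgery, or under anaesthesia, can also carry an effect of the brace if one arm has been wearing it and the other has not.

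The outcome list includes preoperative and postoperative questionnaire scores and a quadriceps circumference difference, so preoperative values will naturally be used as references. If part of the treatment effect or of patient expectation already sits in the reference, a change score or a baseline-adjusted comparison is distorted. An observed difference in that measure before surgery can then no longer be read as chance imbalance. A later analysis plan cannot recover a pre-allocation value that was never collected.

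**Working it through.** The protocol gives no figure on this point to reproduce, and its sample size does not depend on the order of these steps. The check compares the sections and then works out what a shift would do.

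**1. Where each preoperative measure falls relative to allocation and brace use**

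| Measure | Relative to allocation | Relative to KRONOS wear |
|---|---|---|
| Questionnaires (item 5) | After, as listed | Not fixed: any time before surgery |
| Initial-visit extension (item 3) | Not fixed: listed before consent (item 5), but the KRONOS section speaks of an initial clinic visit after enrolment | Not fixed: fitting is at a visit of the same name |
| Preoperative thigh circumference (item 4) | Not fixed, for the same reason | Not fixed |
| Day-of-surgery extension (item 3) | After | After, under the KRONOS section; not under item 8 if the brace is first fitted that day after the reading |
| Under-anaesthesia extension (item 3) | After | After, under the KRONOS section; not under item 8, which places braces at the end of the operation |

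Remote consent sharpens the problem. If a patient signs by email and is allocated then, any clinic measurement made after consent is also made after allocation. Only a standard-of-care measurement taken before consent would precede it.

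**2. Effect of a shift**

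Let d be the average shift in the preoperative value of the KRONOS arm caused by allocation or brace use, T the true between-arm difference in the postoperative value, and b the within-arm slope of the postoperative on the preoperative value.

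- Postoperative values compared directly: expected difference T, bias 0.
- Change from the preoperative value: expected difference T − d, bias −d.
- Adjustment for the preoperative value: expected difference T − b × d, bias −b × d.

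For b between 0 and 1, the bias lies between 0 and d in size. If the preoperative shift is favourable, the bias runs against KRONOS; if unfavourable, it runs in its favour.

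**3. Illustrations (d and b are assumptions; the protocol gives neither)**

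- Extension, d = 2 degrees: a change score is off by 2 degrees. An adjusted comparison is off by 0 to 2 degrees as b runs from 0 to 1. The loss counted in the power calculation is 2 degrees or more.
- A 0–100 knee score, d = 5 points and b = 0.5: 0.5 × 5 = 2.5 points. Over b from 0 to 1 the range is 0 to 5 points.
- d = 0: no bias in any of the three analyses.

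**4. Balance check**

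With 20 per arm, the standard error of a between-arm difference in baseline means is √(1/20 + 1/20) = √(2/20) = 0.32 SD. Chance differences of up to about two standard errors, 2 × 0.32 = 0.64 SD, are therefore unremarkable. For a measure taken after allocation, such a difference cannot be separated from an early effect of allocation or brace use.

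**The case against.** The case against rests on several correct readings, and they limit the point.

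- *A reader might infer that the questionnaires are completed after KRONOS wear.* The text does not say so. Item 5 requires only completion before surgery, and the Preop column has no internal order, so completion at the consent visit before fitting is compatible with it. The questionnaires are also called standard of care, so the rule against research activity before consent need not hold them back.
- *A reader might infer that there is no clean baseline for extension.* That is also unsupported. The initial-visit reading may be one. The defect is that nothing guarantees it.
- *A reader might infer that the primary comparison is biased.* It is not, at least directly. It uses the other knee as reference, and the analysis section names chi-squared, t and Wilcoxon tests without a change-from-baseline or adjusted analysis.
- *A reader might infer that a baseline table becomes worthless.* Age, sex, BMI and laterality cannot be altered by knowing the arm. Only the shiftable measures lose their value.
- *Preoperative exposure rests on the KRONOS section and Table 1.* Item 8, with fitting on the day of surgery, points the other way. If item 8 governs, the one-arm exposure before the later readings largely disappears. The questionnaires would still follow allocation as listed.
- *The protocol does not call the later readings a baseline, and the choice of baseline may sit in an analysis plan that is not shown.* This is true of the label. When a measurement is taken relative to allocation is trial conduct, however, and the protocol is where it is set.

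What stands is that the written order puts allocation before the questionnaires, leaves the first extension and thigh readings unplaced, and contradicts itself on fitting.

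**Conclusion.** The point holds in a limited form. As written, allocation comes before the preoperative questionnaires in a trial with no described blinding. Under the KRONOS Bracing Group section, the day-of-surgery and under-anaesthesia extension readings come after brace use in one arm only. An initial-visit reading could serve as a valid baseline, but its position is not fixed.

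The consequences are confined to pre/post questionnaire and thigh comparisons, any adjustment for preoperative extension, and the balance check on those measures. The primary outcome is not directly affected.

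The size of any shift is unknown and may be zero. The 2-degree and 2.5-point figures illustrate assumed values and are not estimates. The exposure argument assumes that the KRONOS section, not item 8, describes what happens. The argument about knowledge of the arm assumes that patients learn their allocation when it is drawn, which the protocol implies but does not state. The change is worth making because it is cheap and the opportunity passes with each patient randomised.

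**What to change.** In the Consent process section, the Timeline of Events and Table 1, state one order:

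1. signed consent;
2. baseline questionnaires, extension of both knees (goniometer and heel height) and thigh circumference;
3. allocation drawn and disclosed;
4. brace fitting.

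For patients who consent remotely, draw the allocation at the clinic visit once step 2 is complete. Name the step 2 values as baseline, and describe the day-of-surgery and under-anaesthesia readings as post-randomisation data. Split the Preop column of Table 1 so that the order is visible.

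Reconcile the KRONOS Bracing Group section with Timeline of Events item 8 on when the KRONOS brace is fitted, and state whether the initial visit in item 3 is the same as the initial clinic visit in the KRONOS section. This takes no position on preoperative wear or on which fitting time is right; the order above can be followed either way.

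The cost is small, since every step is already planned. The one downside is that remotely consented patients learn their arm at the visit instead of at signature.

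### Only the KRONOS arm is braced before surgery, and the protocol is unclear on when that starts: the trial can compare two bracing regimens but cannot credit a difference to postoperative KRONOS wear

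*Protocol*

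**What the plan says.** **Question.** Purpose of the study sets out to "evaluate the clinical efficacy of the KRONOS postoperative knee brace compared with the standard Breg T-scope hinged brace". The title, the Hypothesis and the Risk/benefit assessment also describe KRONOS as a postoperative brace. None of them mentions bracing before surgery.

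**KRONOS arm.** Under Bracing Protocol, these patients are "measured and fitted with the KRONOS knee brace at their initial clinic visit after study enrollment". The next instruction is "The patient will be instructed to use the brace preoperatively and bring it to their surgery", after which the brace is put back on at the end of the operation.

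**Control arm.** "Subjects will be placed in a standard postoperative hinged knee brace in the operating room that will be locked in full extension". No preoperative brace or matching measure is described.

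**Table 1.** The Brace Placement row has a mark at Preop and another at Surgery. The Preop mark carries a double asterisk, explained as "Only for patients randomized to the KRONOS brace treatment group".

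**Timeline of Events, item 8.** "Subjects will be appropriately fitted for the brace corresponding to randomization on the day of surgery". No exception is made for KRONOS.

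**Randomization.** Under Consent process, it "will occur at the time of informed consent".

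**The concern.** The arms differ in two respects at once: which brace is worn, and whether a brace is worn before the operation. The protocol frames its question around the first and does not mention the second. If KRONOS patients show fewer extension deficits, a report following the stated purpose would credit a postoperative brace with an effect that may partly come from wear before surgery in one arm only. A surgeon who then prescribed KRONOS from the operating room onward would be using a regimen that the trial did not test.

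The differing statements on fitting add to this. Staff who follow item 8 literally would give no preoperative wear. Staff who follow the Bracing Protocol would give an amount that depends on the interval between clinic visit and surgery. What was delivered in the KRONOS arm could therefore vary between patients, and no listed data item records when wear began.

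**Working it through.** The point rests mainly on the text, so the places are set side by side first.

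| Question | KRONOS | T-Scope | Source |
|---|---|---|---|
| When is the arm assigned? | At consent | At consent | Consent process |
| When is the brace first fitted? | Initial clinic visit after enrolment | Operating room (first placement) | Bracing Protocol |
| The same, elsewhere | Day of surgery | Day of surgery | Timeline of Events, item 8 |
| Preoperative placement mark? | Yes | No | Table 1 and footnote |
| Length or hours of preoperative wear? | Not given | None described | Bracing Protocol |

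1. *Is preoperative wear really one-sided?* Yes. The arm descriptions and the Table 1 footnote agree.

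2. *Does it bias the randomized comparison?* No. It follows assignment and so is part of the assigned strategy. The contrast of KRONOS from before surgery with T-Scope from surgery is a fair randomized one.

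3. *Can the postoperative part be isolated?* No. Write the expected difference as D = D(pre) + D(post). Every KRONOS patient is assigned both parts and every control neither. The two arms estimate D only, and a larger sample does not change that.

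4. *Which measurements precede treatment?* Timeline of Events, item 3, schedules range of motion at the initial visit, on the day of surgery and under anesthesia. Under the Bracing Protocol, the last two come after wear has begun in one arm only. The initial-visit value can be an untouched baseline if it is taken before fitting, but the order is not stated.

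**The plan's own figure.** The power analysis uses proportions of 0.545 and 0.091, a difference of 0.454. The two-sided pooled formula, with mean proportion 0.318, gives

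n = [1.96 × √(2 × 0.318 × 0.682) + 0.842 × √(0.545 × 0.455 + 0.091 × 0.909)]² / 0.454² ≈ 15.3,

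which rounds up to 16 per arm, or 32 in total, as stated. This point disputes no figure in the sample size.

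**Illustration on assumed shares.** The protocol gives no value for D(pre). The table supposes that a share f of the planned difference comes from preoperative wear, so that D(post) = 45.4 × (1 − f). The last column is the power of a trial of 20 per arm if it faced that postoperative contrast alone (control rate 0.545, two-sided Fisher test, no dropout).

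| Assumed f | D(post), points | Power |
|---|---|---|
| 0% | 45.4 | 85% |
| 25% | 34.1 | 50% |
| 50% | 22.7 | 20% |

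These rows show how much the reading of the same overall result depends on f. They are not evidence about f, and the trial cannot estimate it.

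**The case against.** **The comparison is randomized, so nothing is confounded.** A reader might infer that one-sided preoperative wear invalidates the trial. The documents do not support that. Randomization takes place at consent, before any brace is worn, and the regimen contrast remains unbiased. What is affected is the label put on the result.

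**Postoperative may simply describe the device.** This is a fair reading of the Background and Hypothesis, and no sentence says that the aim is to isolate wear after surgery. But the purpose and the intended conclusion will be read as being about a brace used postoperatively, and neither mentions preoperative use.

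**The arms differ after surgery too.** The Bracing Protocol sets different rules for how and for how long each brace is worn, so this would be a regimen comparison in any case. That is correct, and it favors regimen wording. Those differences at least fall within the postoperative period named in the purpose; preoperative wear does not.

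**Item 8 may mean a second fitting.** This is possible. The KRONOS brace is put back on after surgery, and Table 1 marks placement at both times, which suggests a two-step sequence. Item 8 does not say so and covers both arms, so the wording needs reconciling even if the intention can be guessed.

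**Baseline is already handled.** Largely so. A reader might infer that day-of-surgery range of motion will serve as baseline and distort the primary result. The protocol never names it as baseline, and the primary outcome is judged against the contralateral knee. Initial-visit measurement is already scheduled. What remains open is whether it precedes fitting.

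**Exposure is partly recorded.** Frequency of brace use is listed as an outcome, and Table 1 appears to place a KRONOS-only compliance survey at surgery. The date of first wear is not listed. Nor can the extra exposure be counted in nights: the interval to surgery is not given, and the night-wear instruction is not tied to the preoperative period.

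**Conclusion.** The point holds as one of attribution and consistency. Preoperative wear of unstated length is assigned to the KRONOS arm only, and item 8 does not match the Bracing Protocol and Table 1 on when KRONOS is first fitted. The comparison of whole regimens is valid. A difference cannot be assigned specifically to postoperative wear of the KRONOS brace.

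The size of the preoperative contribution is unknown. It could be nil, and the shares of 0% to 50% used above are assumptions. The conclusion rests on reading the Bracing Protocol and the Table 1 footnote as the intended schedule. If item 8 alone governed, there would be no preoperative wear and the attribution problem would disappear, but the Bracing Protocol and Table 1 would then be wrong. This review takes no position on which schedule is clinically right. The change is worth making because it decides what the trial may conclude.

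**What to change.** 1. Reconcile the Bracing Protocol, Table 1 with its footnote, and Timeline of Events item 8, so that they agree on when the KRONOS brace is first fitted and first worn. If item 8 describes a second fitting, say so.
2. If preoperative wear stays, word the purpose, hypothesis and intended conclusion as a comparison of two bracing regimens: KRONOS from before surgery versus T-Scope from surgery.
3. State that the already scheduled initial-visit range of motion is measured before any fitting and is the only value used as baseline. Treat day-of-surgery and under-anesthesia values as post-randomization measurements.
4. Record the date of first KRONOS wear, so that the length of preoperative exposure can be reported.

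The cost is some rewording and one date field, with no added visits and no change in sample size. The downside is a narrower claim: the trial would report on the regimens as delivered and not on the brace after surgery alone.
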